8.2 ADVERSE EVENTS AND SERIOUS ADVERSE EVENTS

8.2.1 DEFINITION OF ADVERSE EVENTS (AE)

An adverse event means any untoward medical occurrence associated with the use of an intervention in humans, whether or not considered intervention-related (21 CFR 312.32 (a)).

8.2.2 DEFINITION OF SERIOUS ADVERSE EVENTS (SAE)

An adverse event (AE) or suspected adverse reaction is considered "serious" if, in the view of either the investigator or sponsor, it results in any of the following outcomes:

- 1) Death,
- 2) A life-threatening adverse event,
- 3) Inpatient hospitalization or prolongation of existing hospitalization,
- 4) A persistent or significant incapacity or substantial disruption of the ability to conduct normal life functions, or
- 5) A congenital anomaly/birth defect.

Important medical events that may not result in death, be life-threatening, or require hospitalization may be considered serious when, based upon appropriate medical judgment, they may jeopardize the participant and may require medical or surgical intervention to prevent one of the outcomes listed in this definition. Examples of such medical events include allergic bronchospasm requiring intensive treatment in an emergency room or at home, blood dyscrasias or convulsions that do not result in inpatient hospitalization, or the development of drug dependency or drug abuse.

8.2.3 UNANTICIPATED ADVERSE DEVICE EFFECT

According to 21 CFR 812.3(s), an "unanticipated adverse device effect means any serious adverse effect on health or safety or any life-threatening problem or death caused by, or associated with, a device, if that effect, problem, or death was not previously identified in nature, severity, or degree of incidence in the investigational plan or application (including a supplementary plan or application), or any other unanticipated serious problem associated with a device that relates to the rights, safety, or welfare of subjects."

8.2.4 CLASSIFICATION OF AN ADVERSE EVENT

8.2.4.1 SEVERITY OF EVENT

For adverse events (AEs) not included in the protocol defined grading system, the following guidelines will be used to describe severity.

- **Grade 1 (Mild)** – Events require minimal or no treatment and do not interfere with the participant's daily activities.

- **Grade 2 (Moderate)** – Events result in a low level of inconvenience or concern with the therapeutic measures. Moderate events may cause some interference with functioning.
- **Grade 3 (Severe)** – Events interrupt a participant's usual daily activity and may require systemic drug therapy or other treatment. Severe events are usually potentially life-threatening or incapacitating. Of note, the term "severe" does not necessarily equate to "serious."
- **Grade 4 (Life-Threatening)** - Life-threatening consequences; urgent intervention indicated.
- **Grade 5 (Death)** - Death related to AE.

8.2.4.2 RELATIONSHIP TO STUDY INTERVENTION

All adverse events (AEs) must have their relationship to study intervention assessed by an investigator who evaluates the event based on temporal relationship and his/her clinical judgment. The degree of certainty about causality will be graded using the categories below. In a clinical trial, the study product must always be suspect.

- **Definitely Related** – There is clear evidence to suggest a causal relationship, and other possible contributing factors can be ruled out. The clinical event, including an abnormal laboratory test result, occurs in a plausible time relationship to study intervention administration and cannot be explained by concurrent disease or other drugs or chemicals. The response to withdrawal of the study intervention (dechallenge) should be clinically plausible. The event must be pharmacologically or phenomenologically definitive, with use of a satisfactory rechallenge procedure if necessary.
- **Possibly Related** – There is evidence to suggest a causal relationship, and the influence of other factors is unlikely. The clinical event, including an abnormal laboratory test result, occurs within a reasonable time after administration of the study intervention, is unlikely to be attributed to concurrent disease or other drugs or chemicals, and follows a clinically reasonable response on withdrawal (dechallenge). Rechallenge information is not required to fulfill this definition. "Possibly related" means there is a reasonable possibility that the incident, experience, or outcome may have been associated with the procedures involved in the research. Reasonable possibility means that the event is more likely than not related to participation in the research or, in other words, there is a >50% likelihood that the event is related to the research procedures.
- **Somewhat Likely to be Related** – There is some evidence to suggest a causal relationship (e.g., the event occurred within a reasonable time after administration of the trial medication). However, other factors may have contributed to the event (e.g., the participant's clinical condition, other concomitant events), so there is a <50% likelihood that the event is related to the research procedures. Although an AE may rate only as "somewhat likely to be related" soon after discovery, it can be flagged as requiring more information and later be upgraded to "possibly related" or "definitely related", as appropriate.
- **Unlikely to be Related** – A clinical event, including an abnormal laboratory test result, whose temporal relationship to study intervention administration makes a causal relationship improbable (e.g., the event did not occur within a reasonable time after administration of the study intervention) and in which other drugs or chemicals or underlying disease provides plausible explanations (e.g., the participant's clinical condition, other concomitant treatments).

- **Not Related** – The AE is completely independent of study intervention administration, and/or evidence exists that the event is definitely related to another etiology. There must be an alternative, definitive etiology documented by the clinician.]

8.2.4.3 EXPECTEDNESS

The investigators will be responsible for determining whether an adverse event (AE) is expected or unexpected. An AE will be considered unexpected if the nature, severity, or frequency of the event is not consistent with the risk information previously described for the study intervention.

8.2.5 TIME PERIOD AND FREQUENCY FOR EVENT ASSESSMENT AND FOLLOW-UP

The occurrence of an adverse event (AE) or serious adverse event (SAE) may come to the attention of study personnel during study visits and interviews of a study participant presenting for medical care, or upon review by a study monitor.

All AEs will be captured on the appropriate case report form (CRF). Information to be collected includes event description, time of onset, clinician's assessment of severity, relationship to study device (assessed only by those with the training and authority to make a diagnosis), and time of resolution/stabilization of the event. All AEs occurring while on study must be documented appropriately regardless of relationship. All AEs will be followed to adequate resolution.

Any medical condition that is present at the time that the participant is screened will be considered as baseline and not reported as an AE. However, if the study participant's condition deteriorates at any time during the study, it will be recorded as an AE.

Changes in the severity of an AE will be documented to allow an assessment of the duration of the event at each level of severity to be performed. AEs characterized as intermittent require documentation of onset and duration of each episode.

Research staff will record all adverse events with start dates occurring any time after informed consent is obtained until completion of study participation. At each study visit, the investigator will inquire about the occurrence of AE/SAEs since the last visit. Events will be followed for outcome information until resolution or stabilization.

All new or worsening adverse events (AEs) will be collected for all subjects from the time of subject enrollment through completion or termination of the clinical investigation. This includes AEs that are not device or procedure related.

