history of or current dysplastic Barrett's Esophagus (High Grade Dysplasia (HGD) or Low Grade Dysplasia (LGD)). Cohort B will consist of 20 patients in each of the two groups; current dysplastic Barrett's Esophagus of either High Grade Dysplasia (HGD) or Low Grade Dysplasia (LGD)) and normal controls (with or without history of previous successful esophageal ablation). Classification of patients will occur based on medical history and clinical pathology obtained during the EGD.

Description of Sites/Facilities
Enrolling Participants:

UNC Chapel Hill (Enrolling Site)
Duke University (Device Manufacture)

Description of Study Intervention:

The purpose of this instrument is to obtain optical measurements from the esophageal mucosa via an endoscopic probe. The modalities used by this probe are angle-resolved low-coherence interferometry (a/LCI) and Optical Coherence Tomography (OCT); depth-resolved optical imaging technology. These optical readings provide indications of subsurface tissue architecture and will assist in the detection and diagnosis of metaplastic and dysplastic conditions such as Barrett's esophagus.

The probe is designed to be used in conjunction with the visual guidance provided by a commercial endoscope. The probe has mechanical features similar to a radiofrequency ablation (RFA) "paddle", which is externally attached to an endoscope to provide ablative therapy under visual guidance of the endoscope.

[figure not shown]
Once inserted into a patient's esophagus and placed against the tissue surface, the probe will acquire 2D OCT images of the tissue surface at operator-selected locations. Some of the optical data received will be displayed in real-time. All optical data will also be stored on a computer for post hoc analysis.

During Phase I the OCT instrument will be used alone. The components of the OCT device are grouped into the following modules: 1) Optical probe, 2) OCT engine, 3) computer system and 4) physical enclosure. Phase II of the study will consist of a dual modality a/LCI - OCT combined probe. The combined probe will consist of the following modules: 1) Optical probe, 2) OCT engine, 3) a/LCI engine, 4) computer system and 4) physical enclosure. See section 6.1 for detailed device descriptions.

Study Duration: 24 Months

Participant Duration: 7 days

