8.1.2 ENROLLMENT

The following procedures will be performed during the enrollment visit:

- 1) Re-assess eligibility

- 2) Completion of urine pregnancy test on women with reproductive potential
- 3) Administration of OCT-probe for Cohort A or combined a/LCI-OCT probe for Cohort B and completion of esophageal images during routine care upper endoscopy
- 4) Collection of data from endoscopy
- 5) Collection of co-localized research biopsies (Cohort B)
- 6) Adverse event assessment
- 7) Complete CRFs and data entry

For this study, an enrolled subject is defined as a subject who was successfully administered the OCT device and for whom we have evaluable data.

***Screening and enrollment can occur on the same day.

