8.1.2.3 RESEARCH BIOPSY COLLECTION AND ANALYSIS

For participants enrolled in cohort B, research biopsies will be obtained from the location of device imaging. Research biopsies are taken only if the additional biopsies do not significantly increase the patient's risk or interfere with routine care procedures. The research biopsy protocol may be modified by the physician performing the procedure if necessary. During the procedure up to 10 research biopsies may be taken for use in this study. The total number of research biopsies may vary based on presence/absence of nodularity but will not exceed 10 research-specific biopsies. This number of esophageal biopsies is within the standard of care for biopsying the esophagus. Biopsies will be immediately placed in formalin for processing and histopathological analysis by [name].

Variations to the biopsy protocol (location and number of specimens obtained) are allowable and are not considered protocol deviations.

8.1.3 7 DAY FOLLOW-UP

Enrolled subjects will be contacted 7 days (+/-3 days) after administration of the device via phone or other IRB approved method. Subjects who do not meet the definition of enrolled will not be contacted. During the 7 day follow-up, the following procedures will be performed:

- 1) Assess for adverse events
- 2) Complete eCRF and data entry

No additional follow-up is anticipated.

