
9.3 POPULATIONS FOR ANALYSES

All subjects who were administered the probe, regardless of enrolling cohort, will have data included for optimization unless withdrawn per section 7.2. For this study, an enrolled subject is defined as a subject who was successfully administered the device and for whom we have evaluable data.

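### Section 8.2.5 sets two conflicting adverse-event windows, and a summary based on enrollment can omit events around failed or non-evaluable probe administrations

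*Combined protocol and SAP*

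**What the plan says.** Section 8.2.5 contains two collection rules in consecutive paragraphs. The first is "Research staff will record all adverse events with start dates occurring any time after informed consent is obtained until completion of study participation". The second covers all new or worsening AEs "from the time of subject enrollment through completion or termination of the clinical investigation".

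Enrollment is a defined status. In Section 8.1.2, "an enrolled subject is defined as a subject who was successfully administered the OCT device and for whom we have evaluable data". Section 9.3 repeats the definition for the analysis populations: "an enrolled subject is defined as a subject who was successfully administered the device and for whom we have evaluable data".

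The two end points are also different quantities. The synopsis gives "Participant Duration: 7 days" and "Study Duration: 24 Months". Section 8.1.3 schedules one contact at day 7 (plus or minus 3 days), then states "No additional follow-up is anticipated". On who receives that contact it says "Subjects who do not meet the definition of enrolled will not be contacted".

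Three other provisions bear on the point:
- Section 7.2 says data from withdrawn or terminated subjects will not be used, and allows the investigator to withdraw a subject on the endoscopy findings or for another reason.
- Section 5.4 requires only serious adverse events for subjects who consent but are not entered.
- Section 9.1 promises 95% confidence intervals for all estimates and mentions incidence rates as one example. No section defines a safety population or an AE denominator.

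**The concern.** A device pilot needs a clear account of harm in everyone exposed to the device, including those in whom it did not work. A difficult passage, poor apposition or an abandoned attempt may be just where throat irritation, bleeding or a tear arises. Section 2.3.1 lists such events as ones for which a device contribution may not be excludable.

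If AEs are summarized by the enrollment-based sentence, subjects enter only when the probe worked and the images were usable. The safety summary is then conditioned on technical success. Events in the remaining exposed subjects may be missing from the numerator, and those subjects are missing from the denominator. Two analysts following Section 8.2.5 in good faith could report different AE figures from the same study.

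**Working it through.** **1. The two rules side by side (Section 8.2.5).**

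| | First rule | Second rule |
|---|---|---|
| Start | informed consent | subject enrollment |
| End | end of the subject's participation (7 days, Section 1.1) | end of the investigation (24 months, Section 1.1) |
| Scheduled contact up to the end point? | yes, for enrolled subjects | none after day 7 (Section 8.1.3) |

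**2. Three kinds of consented subject.**

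| Subject | First rule | Second rule, read with the Section 8.1.2 definition | Day-7 contact |
|---|---|---|---|
| Probe administered, data evaluable | covered | covered | yes |
| Probe attempted, failed or not evaluable | covered | not covered | no |
| Consented, probe never attempted | covered (Section 5.4 asks only for serious events) | not covered | no |

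The second row is the gap. These subjects were exposed to the device, but the second rule leaves them out and Section 8.1.3 does not follow them up. If they are withdrawn, Section 7.2 also removes what was recorded on the day. Other text does not settle which rule governs: AE review at screening in the schedule of activities fits the first, while the restricted day-7 contact fits the second.

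**3. Size.** The documents state no AE rate, so there is no figure to reproduce. The following is an illustration only.

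- From the documents: 82 enrolled (3 × 14 + 2 × 20 = 82; Sections 1.1 and 9.2).
- Assumed: 4 enrolled subjects with an AE; a share f of consented subjects who never meet the enrolled definition; a number a of those with an AE.
- Formulas: consented N = 82 / (1 − f), rounded up; enrollment-based proportion = 4/82; consent-based proportion = (4 + a)/N. Intervals are exact (Clopper-Pearson) 95%.

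Enrollment-based: 4/82 = 4.9% (1.3% to 12.0%), whatever happens to the others.

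| f | N | Not enrolled | None has an AE | About 20% do | About 50% do |
|---|---|---|---|---|---|
| 0 | 82 | 0 | 4/82 = 4.9% | same | same |
| 10% | 82/0.9 = 91.1, so 92 | 10 | 4/92 = 4.3% (1.2 to 10.8) | 6/92 = 6.5% (2.4 to 13.7) | 9/92 = 9.8% (4.6 to 17.8) |
| 20% | 82/0.8 = 102.5, so 103 | 21 | 4/103 = 3.9% (1.1 to 9.6) | 8/103 = 7.8% (3.4 to 14.7) | 14/103 = 13.6% (7.6 to 21.8) |

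(20% and 50% of 21 are 4.2 and 10.5, taken as 4 and 10.)

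The direction depends on the omitted subjects. With f = 10%, one AE among the ten gives 5/92 = 5.4%, already above 4.9%. With none, the enrollment-based figure is slightly the higher of the two. The table treats every non-enrolled subject as having had a probe attempt; any who did not would fall outside the denominator recommended here.

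**The case against.** The strongest reply is that nothing need be lost. The first rule already requires every event after consent to be recorded, and collecting from consent satisfies both rules at the start. *Enrollment* is also the name of the visit at which the probe is administered and AEs are assessed (Sections 1.3 and 8.1.2). On that reading, events during passage fall inside the second window too. Much of this stands. A reader might infer that a tear or aspiration during passage would go unrecorded; the documents do not support that, because the first rule captures it. What remains is that no text says which set is tabulated or over which subjects, and the only stated definition of an enrolled subject requires success and decides who is called at day 7.

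A reader might also infer that the later end point makes the device look safer by adding unobserved follow-up time. The documents do not support this either. No person-time AE rate is planned, and Section 9.1 mentions incidence rates only generically. For the proportion of subjects with an event, a later end point cannot lower the result. Section 8.2.5 also allows events to surface when a participant presents for care or at monitor review. The end-point conflict is a wording inconsistency to remove, with no demonstrated bias.

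Finally, the synopsis lists no endpoints and Section 9.4 contains no safety analysis. That limits the weight of the point. It does not remove it: AEs are collected on case report forms, results will be submitted to ClinicalTrials.gov (Section 10.1.11), and any AE summary needs a stated period and population.

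**Conclusion.** The point holds in a limited form. Section 8.2.5 states two windows that disagree at start and end. Taken with the definition of an enrolled subject, the restricted day-7 contact and the exclusion of withdrawn subjects' data, an enrollment-based AE summary can omit events around failed or non-evaluable probe administrations, which would understate device-related AEs.

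The size cannot be derived from the documents. In the 10% illustration, a reported 4.9% corresponds to a consent-based figure between 4.3% and 9.8%. This rests on the assumed 4 subjects with an AE, the assumed non-enrolled share and the assumed AE frequency among those subjects. The start-side effect is zero if every consented subject becomes enrolled and no event precedes enrollment. The change should be made, but the point does not threaten the study's imaging objectives.

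**What to change.** - **Section 8.2.5.** Delete the sentence that runs from enrollment to the end of the investigation. State one window for tabulation: informed consent through the day-7 contact. Report the proportion of subjects with an AE among all in whom probe passage was attempted, with exact 95% confidence intervals. List later spontaneous reports separately, outside that proportion.
- **Section 8.1.3.** Extend the day-7 contact to subjects in whom the probe was attempted but who do not meet the enrolled definition.
- **Section 7.2.** Exempt safety data from the rule that withdrawn subjects' data are not used.

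The cost is short edits to three sections, a few extra phone calls and a possibly less favorable AE figure. No new clinic visit is needed. Editing Section 8.2.5 alone would not be enough: without the other two changes, attempted-but-not-enrolled subjects would be in the denominator with no day-7 information.

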8.2.6 ADVERSE EVENT REPORTING

Research staff will maintain records of all adverse events and report them in a timely manner via completion of the Adverse Event Case Report Form. The form should be updated with any changes including updates to severity, relatedness, and resolution. Adverse events will be reported to the UNC IRB per UNC IRB reporting requirements.

Events will be described using the NCI Common Terminology Criteria for Adverse Events (CTCAE).

8.2.7 OTHER SAFETY REPORTING

Sites may have additional safety reporting requirements or reporting requirements that differ from those outlined in this protocol. Sites are responsible for complying with requirements outlined in this protocol, as well as any local reporting requirements and definitions.

8.2.8 REPORTING EVENTS TO PARTICIPANTS

Not applicable. Participation involves a one-time visit. Safety information will be reviewed as part of the initial consent process, and consent will be obtained with new safety information as applicable.

8.2.9 EVENTS OF SPECIAL INTEREST

Not applicable.

8.2.10 REPORTING OF PREGNANCY

Not applicable.

8.3 UNANTICIPATED PROBLEMS

8.3.1 DEFINITION OF UNANTICIPATED PROBLEMS (UP) AND UNANTICIPATED ADVERSE DEVICE EFFECT (UADE)

The Office for Human Research Protections (OHRP) considers unanticipated problems involving risks to participants or others to include, in general, any incident, experience, or outcome that meets all of the following criteria:

- Unexpected in terms of nature, severity, or frequency given (a) the research procedures that are described in the protocol-related documents, such as the Institutional Review Board (IRB)-approved research protocol and informed consent document; and (b) the characteristics of the participant population being studied;
- Related or possibly related to participation in the research (“possibly related” means there is a reasonable possibility that the incident, experience, or outcome may have been caused by the procedures involved in the research, reasonable possibility means that the event is more likely than not related to participation in the research or, in other words, there is a >50% likelihood that the event is related to the research procedures); and

- Serious or suggests that the research places participants or others at a greater risk of harm (including physical, psychological, economic, or social harm) than was previously known or recognized.

According to 21 CFR 812.3(s), an unanticipated adverse device effect means any serious adverse effect on health or safety or any life-threatening problem or death caused by, or associated with, a device, if that effect, problem, or death was not previously identified in nature, severity, or degree of incidence in the investigational plan or application (including a supplementary plan or application), or any other unanticipated serious problem associated with a device that relates to the rights, safety, or welfare of subjects (21 CFR 812.3(s)).

